### **8.3 Primary Efficacy Endpoint(s) and Analyses**

#### **8.3.1 Primary Efficacy Endpoint(s)**

The primary endpoint is the percentage of responders, defined as subjects meeting the following two conditions:

- MBL volume < 80 mL at the Final Month, and
- 50% or greater reduction in MBL volume from Baseline to the Final Month

Subjects whose primary reason for prematurely discontinuing study drug is "lack of efficacy," or "requires surgery or invasive intervention for treatment of uterine fibroids" will be considered as non-responders.

#### **8.3.2 Handling of Missing Data for the Primary Efficacy Endpoint(s)**

See Section 8.2 for the handling of missing data for the primary analysis and sensitivity analyses for the primary efficacy endpoint.

#### **8.3.3 Primary Efficacy Analysis**

The primary analysis of the primary endpoint will be performed using the full analysis set population.

If a subject has missing observed Final Month MBL volume, the Final Month MBL volume will be imputed using multiple imputation as described in Section 8.2.

The primary analysis of the primary efficacy endpoint with multiple imputation will be carried out in the following steps:

1. **Multiple Imputation:** 30 "complete" datasets of monthly MBL volume from Month 1 to Month 6 will be generated using SAS PROC MI as described above. The following covariates will be used in the imputation model:
  - a. Baseline MBL volume

- b. Randomized treatment group
  - c. Baseline hemoglobin
  - d. MBL volume in prior months
  - e. Age of the subject at Baseline
2. **Impute Final Month MBL Volume:** In each of the 30 generated datasets, subject's missing Final Month MBL volume will be imputed using the MBL volume from the "complete" dataset with Month 1 – 6 MBL volume by looking at the corresponding month of the last dose day using analysis time window. Subjects whose last dose day are the same as Study Day 1 will have their Final Month MBL volume imputed using their Month 1 MBL volume.
3. **Impute Responder Status:** The responder status (yes/no) will be derived from "complete" (observed or imputed) Final Month MBL volume, using the criteria as described in Section 8.3.1. Subjects whose primary reason for prematurely discontinuing study drug is "lack of efficacy," or "requires surgery or invasive intervention for treatment of uterine fibroids" will be considered as non-responders.
4. **Analysis:** Each of the 30 imputed datasets will be analyzed separately using a logistic regression model including treatment as the main effect and Baseline MBL volume as a covariate to compare the elagolix treatment group to placebo.
5. **Pooling:** Estimates of the proportions of responders in each treatment group and the difference between the proportions from the 30 imputed datasets obtained from step 3 will be combined into one overall result using PROC MIANALYZE in SAS.

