4 INVESTIGATIONAL PLAN

4.1 Overall Study Design and Plan

This is a Phase 4, randomized, double-blind, 6-month placebo-controlled, parallel-group, multicenter study. Premenopausal women 18 to 51 years of age with uterine fibroids and HMB, as evidenced by MBL > 80 mL during 1 menses in Screening as measured by the alkaline hematin method, will be selected for this study. See [Section 5.1](#) for information regarding eligibility criteria.

Once eligibility is established during the Screening Period, eligible subjects will be randomly assigned in the double-blind period at the baseline visit to receive either elagolix 150 mg QD or placebo in a 2:1 ratio for 6 months. Following the double-blind Treatment Period, there will be a 1 month Post-

[figure not shown]
Treatment Follow-Up (PTFU) Period. The study will be conducted in approximately 45 sites in the US (including Puerto Rico).

Total study duration can be up to 9 months (Screening Period of approximately 1.5 to 2.5 months prior to Study Day 1 [Baseline]). The study consists of the following 4 study periods:

- Washout Period: up to 10 months prior to Screening (only applicable if subject is taking exclusionary medication at the time of consent); duration is based on the excluded medication (Table 1).
- Screening Period: approximately 1.5 to 2.5 months prior to Study Day 1 (Baseline). Screening-related procedures to assess for eligibility must be conducted within first 1.5- to 2.5-month duration. However, in the event the cycle or product collection is not complete within 2.5 months during the Screening Period, the Screening Period may be extended with prior approval from AbbVie therapeutic area medical director (TA MD) and would result in a longer duration of participation for the subject than outlined.
- Treatment Period: duration of 6 months (double-blind). For all subjects who meet eligibility criteria during the Screening Period, each subsequent visit during the Treatment Period should be scheduled based on the date of the Day 1 (randomization) visit.
- PTFU Period: One month following the last dose of study drug. All subjects are expected to enter the 1-month PTFU after completing Treatment Month 6 or once a subject prematurely discontinues from the treatment period.

The schematic of the study is shown in Figure 1. Further details regarding study procedures are located in Appendix F, Operations Manual.

Figure 1. Study M16-824 Schematic

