2.2 Individual Treatment Period Visit Activities

This section presents a list of activities performed during the Treatment Period, organized by visit. The dot pattern depicted at the beginning indicates the place of the visit in the overall Treatment Period Activity Schedule. There are 10 dots representing the 10 visit types that are associated with the treatment Period beginning with Day 1 (Baseline), Month 1 to 6, Premature Discontinuation (PD), Product Collection Visit, and Unscheduled Visit (UNSCH).

Scheduled monthly visits during the Treatment Period are based on a 28-day month. Month 1 through 5 visits must occur within ± 5 days of the projected date. A -5 or +6 days visit window will be allowed in order to collect sanitary products from the last episode of menstrual bleeding or spotting prior to the Month 6 visit if menstrual bleeding starts immediately prior to or coincides with the scheduled visit. The subject will be instructed to continue taking study drug from the extra blister card until she returns for the Month 6 visit.

In the event that a subject or study personnel cannot come to the site because of the COVID-19 pandemic, study visits may be conducted over the phone where feasible, and AbbVie should be notified.

Activities are grouped by category (Interview, Exam, etc.). Further information about each activity is provided in Section 3.

Day 1 (BASELINE):

 INTERVIEW	
 • Eligibility criteria • Medical history (including tobacco and alcohol use) • Symptom-directed gynecological/obstetrical history 	
 • AE assessment • Prior/concomitant therapy • Physician Surgery Questionnaire (PSQ)
 EXAM	
 • Contraception counseling/dispense contraceptives as necessary • Birth control attestation • Vital signs 	
 • Symptom-directed physical exam • Dispense sanitary products collection kit (keg, collection bag, etc.) • Return sanitary products
 PRO	
 • Reason for Study Participation Questionnaire • C-SSRS Baseline/Screening 	
 • Uterine Fibroid Symptoms Quality of Life (UFS-QoL)
 LAB	
 • Urine pregnancy test (if positive, perform a serum pregnancy test) 	
 • Draw venous blood sample (if a keg is returned)

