## **6.0 Study Drug Duration**

For the safety analysis set population, duration of treatment will be summarized for each treatment group and for both groups combined. Duration of treatment is defined for each subject as last dose date minus first dose date + 1. Duration of treatment will be summarized using the number of subjects treated, mean, standard deviation, median, minimum and maximum. In addition, the number and percentage of subjects treated with study drug for a duration in each treatment duration interval (1 – 28 days, > 28 – 56 days, > 56 – 84 days, > 84 – 112 days, > 112 – 140 days, > 140 – 168 days, > 168 days) will be summarized.

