### **8.2 Handling of Missing Data**

Multiple Imputation (MI) will be used in the primary analysis for the primary endpoint.

Missing Final Month MBL volume will be imputed using multiple imputation. First, *M* "semi complete" datasets of monthly MBL volume (Month 1 [Day 2 – Day 28], Month 2

[Day 29 – Day 56], Month 3 [Day 57 – Day 84], Month 4 [Day 85 – Day 112], Month 5 [Day 113 – Day 140], and Month 6 [Day 141 – Day 168]) with monotone missing data pattern will be generated via MCMC option using SAS PROC MI. Then, for each of the  $M$  "semi complete" datasets with monotone missing data, a "complete" dataset of monthly MBL volume from Month 1 to Month 6 will be generated via MONOTONE REG option using SAS PROC MI.  $M$  represents the number of imputations and we set  $M = 30$ . The random seed 12345 will be used.

Mixed-Effect Model Repeat Measurement (MMRM) will be used for the analyses of change and percent change from Baseline in MBL volume to each month. The repeated measures analysis will be conducted using a mixed model including observed measurements at all visits for each month being analyzed. The mixed model includes the categorical fixed effects of treatment, month and treatment-by-month interaction, and the continuous fixed covariate of baseline measurement. The REPEATED statement will be used for month in PROC MIXED with blocks in the covariance matrix identified by subject nested within treatment group. An unstructured variance covariance matrix will be used. Parameter estimation is based on the assumption of data being missing at random and using the method of restrictive maximum likelihood (REML).

Missing data will be imputed using the following methods for the sensitivity analyses of the primary efficacy endpoint:

- Non-Responder Imputation (NRI): All subjects who have missing Final Month MBL volume will be considered as non-responders.
- Observed Cases (OC): The OC analysis will not impute values for missing evaluations, and thus subjects who have missing Final Month MBL volume will be excluded from this analysis.

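### Does step 2 of the primary imputation leave a completer who dosed past Day 168 without a Final Month value?

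*SAP*

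**What the plan says.** SAP 8.3.3 runs the primary analysis on the full analysis set and states that a missing Final Month MBL is to be imputed. Step 1 completes the monthly volumes for Months 1 to 6. Step 2 then picks one of those months for each woman with a missing Final Month, "by looking at the corresponding month of the last dose day using analysis time window".

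SAP 8.2 gives the windows, ending "and Month 6 [Day 141 – Day 168]) with monotone missing data pattern". Month 1 starts on Day 2, so a last dose on Day 1 lies outside every window. Step 2 covers that edge: "Subjects whose last dose day are the same as Study Day 1 will have their Final Month MBL volume imputed" from Month 1. It has no matching sentence for a last dose after Day 168.

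Such last doses can occur:
- Protocol 4.1 says that "each subsequent visit during the Treatment Period should be scheduled based on the date of the Day 1 (randomization) visit". Operations Manual 2.2 counts months as 28 days.
- The same section adds for Month 6: "A -5 or +6 days visit window will be allowed in order to collect sanitary products". The allowance applies if bleeding starts just before, or coincides with, the scheduled visit. The woman is told to "continue taking study drug from the extra blister card until she returns for the Month 6 visit".
- SAP 6.0 has treatment-duration categories that end "> 140 – 168 days, > 168 days".

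SAP Table 2, which serves the amenorrhea and suppression summaries, has an open-ended last row that starts at Day 141.

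**The concern.** The look-up depends on the last dose day falling inside a listed month. A compliant completer can take her last dose after Day 168 and so fall inside none. If her Final Month MBL is also missing, a literal program finds no volume. Step 3 then cannot set responder status, and the logistic model drops her without notice.

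That would remove from the primary analysis some of the women whom the imputation is meant to keep. The same step feeds sensitivity analyses 1 and 4, the two component analyses, the Final Month ANCOVA and the subgroup summaries. In a trial of 48, each woman is 1/32 = 3.1% of the elagolix arm or 1/16 = 6.3% of the placebo arm. The loss might not be neutral, because the late window is given for bleeding. Missing collection is also foreseeable, since during the pandemic "study visits may be conducted over the phone where feasible".

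That step 2 repairs the Day 1 edge makes the silence at the other edge look like an oversight.

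**Working it through.** **1. The plan's own sample size.** Inputs from SAP 2.4: 10% vs 55%, 2:1 allocation, two-sided 0.05, 80% power. Pooled rate = (0.10 + 2 × 0.55)/3 = 0.40.

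Placebo n without continuity correction = [1.960 × √(1.5 × 0.40 × 0.60) + 0.842 × √(0.10 × 0.90 + 0.55 × 0.45/2)]² / 0.45² = 12.1.

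With continuity correction = (12.1/4) × [1 + √(1 + 6/(12.1 × 2 × 0.45))]² = 15.3, rounded up to 16. Then 16 + 32 = 48, as stated.

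**2. Which last dose days fall outside Months 1–6.** The documents give no study-day number for the Month 6 visit, so I assume Day 168 (6 × 28) or Day 169 (Day 1 + 168), with the last dose on the visit day or the day before. Last dose day = planned day + offset (−5 to +6) − lag (0 or 1).

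| Planned day | Lag | Range of last dose day | Offsets after Day 168, of 12 |
|---|---|---|---|
| 168 | 0 | 163–174 | 6 |
| 168 | 1 | 162–173 | 5 |
| 169 | 0 | 164–175 | 7 |
| 169 | 1 | 163–174 | 6 |

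These count calendar offsets. They are not the share of women affected, because the window is conditional on bleeding around the visit. An on-time visit is affected only with Day 169 and a dose that morning.

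**3. Which month fits.** SAP 8.1 defines the Final Month as the 28 days ending on the last dose day, so for last dose day d it runs from d − 27 to d. Its overlap with Days 141–168 is 168 − (d − 27) + 1 = 196 − d days when d > 168.
- d = 169: 27 of 28 days
- d = 174: 22 of 28 days
- d = 175: 21 of 28 days

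No other defined month overlaps at all, since Month 5 ends on Day 140.

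**4. How many women.** Two conditions must both hold: a last dose after Day 168 and no observed Final Month MBL. SAP Appendix D assumes about 90% with observed data, so 48 × 10% = 4.8 are missing for any reason. The range is 0 to about 5. The upper end needs every missing woman to be a late-dosing completer, yet the 10% includes early discontinuers, whom step 2 already maps.

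**5. Cost if they were dropped.** Exact enumeration of binomial outcomes at 55% vs 10%, with an unadjusted likelihood-ratio test standing in for the logistic model (no baseline covariate, no pooling over imputations):
- 32:16: power 91.9%
- 29:14 (five lost): power 88.9%

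Near the planned rates, 18/32 vs 2/16 gives p = 0.0023. Dropping any one woman gives p between 0.0005 (placebo responder) and 0.0036 (placebo non-responder). Over all outcomes at the planned rates, losing one woman at random changes significance in about 1.6% of trials, given that a loss occurs.

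**The case for a change.** The strongest case for a change is that the derivation of a primary endpoint should be written down before unblinding, not settled in code. The authors saw that an unmapped last dose day needs a rule, and wrote one for Day 1 only. One woman can also matter near the boundary. With assumed results of 12/32 vs 2/16, p = 0.060, and losing one placebo responder (12/32 vs 1/15) gives 0.017. With 18/32 vs 4/16, p = 0.037, and losing one placebo non-responder (18/32 vs 4/15) gives 0.054.

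The textual gap stands. The consequence drawn from it does not, for four reasons.
- A reading that leaves a woman without a value contradicts the instruction in the same section to impute a missing Final Month in the full analysis set. With six months available and one adjacent, there is no competing choice to settle.
- The boundary examples are real arithmetic on results picked to lie at the boundary. The 1.6% figure is the fairer guide, and it still supposes that a woman is lost.
- The extra days exist so that products from a late bleed can be collected, so the women who use them are not an obvious group to lack MBL. For those who cannot attend because of the pandemic, Operations Manual 3.22 allows a home health care service to obtain the products and the venous sample.
- The non-responder sensitivity analysis in SAP 8.3.4 keeps every such woman. A silent drop in the primary analysis would show as a difference in denominators.

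One limit remains. If a woman's uncollected bleed began after Day 168, a low Month 6 volume would miss it and could class her as a responder. That is a property of using Month 6, and writing the rule down would not remove it.

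**Conclusion.** No change is needed. The SAP leaves unsaid which month serves a last dose after Day 168, but its own imputation rule and windows leave only Month 6, and the open-ended last row of Table 2 treats later days the same way. A competent analyst would code it so, and an added sentence would give the same numbers.

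The expected effect on the primary result is little or none. In the worst case, with a literal program and all of about five missing women being late-dosing completers, power falls from 91.9% to 88.9%, above the planned 80%. This rests on the SAP's 90% observed-data assumption, the planned rates of 55% and 10%, and an unadjusted test in place of the covariate-adjusted, multiply imputed model. The documents do not give the number of women who will both dose past Day 168 and lack Final Month MBL. Women with an observed Final Month are unaffected. Protocol Appendix E now describes the study as exploratory, which further lowers the stakes.

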### 8.3.4 Additional Analyses of the Primary Efficacy Endpoint(s)

#### Sensitivity Analyses

The sensitivity analyses for the primary endpoint use different approaches to handle prematurely discontinued subjects, missing Final Month MBL volume, and AH data from validated versus unvalidated products.

The analysis set used for sensitivity analyses is the full analysis set. Each of the following sensitivity analyses for the primary endpoint will be performed using a logistic regression model including treatment as the main effect and Baseline MBL volume as a covariate to compare the elagolix treatment group to placebo.

Unless otherwise specified, subjects whose primary reason for prematurely discontinuing study drug is "lack of efficacy," or "requires surgery or invasive intervention for treatment of uterine fibroids" will be considered as non-responders.

1. The primary analysis will be repeated with all subjects categorized as responders/non-responders based on observed or imputed MBL volume data only (without taking into account their reasons for premature discontinuation of study drug). Multiple imputation will be performed the same way as in the primary analysis.
2. Non-responder imputation (NRI): All subjects who have missing Final Month MBL volume will be considered as non-responders. No multiple imputation will be performed.
3. Observed cases: The primary analysis will be repeated with the observed Final Month MBL volume. Subjects who have missing Final Month MBL volume will be excluded from this analysis.
4. The primary analysis will be repeated using the total MBL volume collected from validated products only. All subjects will be categorized as responders/non-responders in the same manner as done in the primary analysis (i.e., using the

multiple imputation described in Section 8.3.3) with the exception that all AH data (including that for Baseline MBL volume) will be based on the total MBL volume collected from validated products only.

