5.5 Withdrawal of Subjects and Discontinuation of Study

The investigator may discontinue a subject from the study at any time if the investigator considers it necessary for any reason, including the occurrence of an AE or noncompliance with the protocol. Subjects who withdraw from the study will not be replaced unless the investigator and AbbVie mutually agree in writing. Subjects may voluntarily withdraw or will be withdrawn from study drug treatment and/or the study at any time for reasons including, but not limited to, the following:

- The subject decides to withdraw consent for any reason.

- The investigator believes it is in the best interest of the subject.
- Clinically significant deterioration of the subject's medical status as determined by the investigator.
- The subject requires surgical intervention for treatment of uterine fibroids and menstrual bleeding or other procedures including hysterectomy, myomectomy, uterine artery embolization, high-intensity focused ultrasound (HIFU), endometrial ablation, dilation and curettage (D&C), etc. during the Treatment Period. In the post treatment period, these procedures do not warrant withdrawal if performed during the PTFU Period unless a hysterectomy with bilateral salpingo-oophorectomy (BSO) is performed and the subject does not plan to use hormone replacement therapy within 1 month of the surgery date.
- The subject becomes pregnant or has a positive serum pregnancy test.
- The subject has ALT or AST elevation $\geq 5 \times$ upper limit of normal (ULN), confirmed upon repeat testing during the Treatment Period.
- The subject develops clinically significant gynecological findings or condition that in the investigator's or AbbVie TA MD's opinion would preclude the subject from continuing in the Treatment Period due to safety reasons.
- If subject experiences a nontraumatic bone fracture during Treatment Period.
- In the investigator's opinion, the subject is unable or unwilling to comply with study-related assessments and procedures.
- Any other medical reason that AbbVie or the investigator deems appropriate.

For subjects to be considered lost to follow-up, reasonable attempts must be made to obtain information on the subject's final status. At a minimum, 2 telephone calls must be made and 1 certified letter must be sent and documented in the subject's source documentation.

Treatment Interruption

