7.3 Statistical Analyses for Efficacy

Primary Efficacy Analysis

The primary efficacy analysis will be based on the FAS, and the primary endpoint will be the proportion of responders meeting the following conditions:

- MBL volume < 80 mL at the Final Month (the last 28 days of treatment)
- $\geq 50\%$ reduction in MBL volume from Baseline to Final Month (the last 28 days of treatment)

Subjects whose primary reason for prematurely discontinuing study drug is "lack of efficacy," or "requires surgery or invasive intervention for treatment of uterine fibroids" will be considered as non-responders.

The primary endpoint will be analyzed using a logistic regression model including treatment as the main effect and baseline MBL volume as a covariate. Missing Final Month MBL volume will be imputed using multiple imputation. For subjects who prematurely discontinue the Treatment Period prior to Month 6, the Final Month (the last 28 days prior to and including the last dose date) will be used in the primary analysis.

Additional Efficacy Analyses

Details on other efficacy analyses are provided in the SAP.

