## **8.0 Efficacy Analyses**

### **8.1 General Considerations**

All efficacy analyses will be conducted in the FAS Population. All tests will be 2-sided at an alpha level of 0.05.

Unless otherwise specified, categorical data will be summarized by frequency and percentage; descriptive summaries of continuous data will display the mean, SD, median, minimum, and maximum.

For continuous variables, when the analyses of change and/or percent change from Baseline to post-baseline visit(s) are performed, the within-group change from Baseline to each applicable visit will be summarized by treatment group with the mean, SD (or SE), and 95% Confidence Intervals (CIs). The between-group differences will be summarized with the mean, SE, 95% CIs, and P value when applicable. At each post-baseline visit, the Baseline mean and post-baseline visit mean will be calculated for all subjects with baseline and post-baseline value at that visit by treatment group.

Final Month is defined as the last 28 days prior to and including the last dose day.

Unless otherwise specified, there is no hypotheses testing for efficacy endpoints in the Post-Treatment Follow-up Period.

Information regarding corresponding statistical methods for analyses and any additional statistical measures required for a specific variable/endpoint will be provided in relevant sections.

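### No planned comparison counts early stopping as failure: a woman who stops for an adverse event with a qualifying observed Final Month stays a responder in the primary and sensitivity analyses

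*SAP*

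**What the plan says.** **The window.** SAP 8.1 states: "Final Month is defined as the last 28 days prior to and including the last dose day". Protocol 7.3 applies the same window to early stoppers in a sentence that opens "For subjects who prematurely discontinue the Treatment Period prior to Month 6, the Final Month". An early stopper is thus judged on her own last 28 days on drug, not on Month 6.

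**Forced failures.** Protocol 7.3 and SAP 8.3.1 force non-response for two primary reasons for stopping: lack of efficacy, and surgery or invasive intervention for fibroids. Protocol 5.5 lets the investigator discontinue a subject "for any reason, including the occurrence of an AE or noncompliance with the protocol", but adverse events are not on the forced-failure list.

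**Missing values.** SAP 8.3.3 fills a missing Final Month from the imputed monthly data "by looking at the corresponding month of the last dose day using analysis time window", so again not from Month 6.

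**Sensitivity analyses (SAP 8.3.4).** The section opens by saying that these analyses "use different approaches to handle prematurely discontinued subjects", among other things.
- Analysis 1 classifies women on volume alone, "without taking into account their reasons for premature discontinuation of study drug".
- Analysis 2 is non-responder imputation (NRI): "All subjects who have missing Final Month MBL volume will be considered as non-responders".
- Analysis 3 uses observed Final Month values and excludes women without one.
- Analysis 4 repeats the primary rule on volume from validated products only.

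**The concern.** The treatment under test is a 6-month course. If the drug reduces bleeding and also causes some women to stop for side effects, those women can enter the responder count on the strength of their last 28 days on drug. A reader who asks what share of women both finished the course and had their bleeding controlled will find no modelled answer.

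The sentence introducing the sensitivity analyses suggests that the handling of discontinued subjects is stress-tested. It is varied in one direction only. Analysis 1 withdraws the one existing failure rule, so within each arm it can only add responders. No analysis makes the rule stricter.

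With 32 and 16 women, a handful of such cases could alter how firmly the result can be stated.

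**Working it through.** **Step 1. Trace one woman.** She stops for an adverse event in Month 3.

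| Analysis | Final Month observed, both criteria met | Final Month missing |
|---|---|---|
| Primary | Responder | Imputed; can be a responder |
| 1. Stop reasons ignored | Responder | Imputed; can be a responder |
| 2. NRI | Responder | Non-responder |
| 3. Observed cases | Responder | Excluded |
| 4. Validated products | Responder if that volume also qualifies | Imputed; can be a responder |

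The gap is therefore specific to women with an observed, qualifying Final Month.

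**Step 2. Look for another analysis that fills it.**
- The component analyses (SAP 8.3.4, Additional Analyses) reuse the primary and sensitivity methods.
- The Bayesian supportive analysis (SAP Appendix D) uses the same primary endpoint.
- The repeated-measures analysis by month (SAP 8.4) leaves early stoppers out of the affected intervals; it does not fail them.
- The cumulative amenorrhea summary (SAP 8.4) carries a stopper's favourable status forward.

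None counts early stopping as failure.

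**Step 3. Reproduce the design figure.** Inputs from Protocol 7.7 and SAP 2.4: 32 elagolix, 16 placebo, response 55% and 10%, two-sided alpha 0.05, power at least 80%. The continuity-corrected two-proportion formula at 80% power gives 16 + 32 = 48, an exact match. Power at 32:16 is 82.7% (continuity-corrected), 86.5% (exact Fisher) or 91.1% (pooled z). The stated figure holds, with an assumed difference of 55 − 10 = 45 points.

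**Step 4. Weight of one woman.** One elagolix responder reclassified is 1/32 = 3.1 points. One placebo responder is 1/16 = 6.25 points, in the opposite direction for the difference.

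**Step 5. Assumed range.** The documents give no discontinuation rate. The nearest figure, about 90% with observed primary endpoint data (SAP Appendix D), concerns missing data and not stopping. Let f be the share of responders in each arm who stopped early for a reason not already failed.

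| f | Elagolix 0.55 × (1 − f) | Placebo 0.10 × (1 − f) | Difference |
|---|---|---|---|
| 0 | 55% | 10% | 45 points |
| 10% | 49.5% | 9% | 40.5 points |
| 20% | 44% | 8% | 36 points |

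**Step 6. Whether the conclusion could move.** The whole-number counts nearest the design rates are 18/32 (0.55 × 32 = 17.6) and 2/16 (0.10 × 16 = 1.6). Two-sided Fisher p-values, as a simple stand-in for the planned logistic model, are:
- 18/32 vs 2/16: p = 0.005.
- 14/32 vs 2/16 (four elagolix responders lost, no placebo responder lost): p = 0.050.
- 14/32 vs 1/16 (about the 20% row, both arms affected): p = 0.009.

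Only the one-sided loss reaches the threshold.

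**The case against.** **The endpoint is a choice, not a mistake.** The on-treatment Final Month is defined consistently in both documents, the objective is reduction of heavy bleeding, and tolerability is reported separately. Failing every stopper, including women who leave for unrelated reasons, mixes retention with bleeding control. This stands: the point is a missing supplementary analysis. A reader might infer that the primary analysis is wrong, and the documents do not support that.

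**Not every analysis keeps her.** A reader might infer that an early stopper is a responder under all four sensitivity analyses whatever her data. If her Final Month is missing, NRI fails her and observed cases drops her.

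**Analysis 1 need not favour elagolix.** It lifts the failure rule in both arms. Stops for lack of efficacy could be commoner on placebo, where each woman weighs twice as much. Its effect on the difference can go either way. For the same reason, analysis 1 and a stricter analysis bracket each arm's responder rate but need not bracket the treatment difference.

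**The SAP does not contradict itself.** Its sentence names three things to vary, and analysis 1 does vary the first. No worst-case rule is promised.

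**Some of the information is planned.** By arm, the SAP gives discontinuations by primary reason (5.0), treatment duration (6.0), adverse events leading to discontinuation (9.2.4) and a cross-tabulation of the two bleeding criteria for each 28-day interval (8.3.4). A reader could build a crude Month 6 count from these. No estimate, interval or test is planned for it, so this is only a partial answer.

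**The study is small and exploratory.** Protocol Appendix E says so. That limits the urgency, not the usefulness, of a single added run.

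**Conclusion.** The point holds as a gap in the sensitivity analyses. A woman who stops early for an adverse event, or for any reason other than the two listed, and whose observed Final Month meets both criteria is a responder in the primary analysis and in sensitivity analyses 1 to 3, and conditionally in 4. No planned comparison counts her as a failure.

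The size cannot be fixed from the documents. The 40.5 and 36 points rest on assumed shares of 10% and 20%, equal in both arms. The move from p = 0.005 to p = 0.050 rests on a loss of four responders confined to elagolix, and nothing in the documents indicates that this will occur. If few women stop, the effect will be small. Nor do these figures show an underpowered trial: the sample size reproduces, and the primary analysis would not change. This is a cheap improvement worth making, not a defect that invalidates the plan.

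**What to change.** Add one sensitivity analysis to SAP 8.3.4: full analysis set, same logistic model, every premature discontinuation of study drug for any reason classed as non-response, and multiple imputation kept for completers with a missing Final Month. Beside it, tabulate the responders who stopped early by arm and reason, so that a reader can separate adverse events from unrelated departures. Do not describe the new analysis and analysis 1 as bounds on the treatment difference. Specify it before unblinding, since it would otherwise be post hoc.

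The cost is a paragraph, one model run and a small table. The downside is a conservative figure that combines retention with bleeding control and will usually be less favourable. With so few placebo responders expected, reclassification could leave none, in which case the logistic model may have no finite estimate; the raw counts and the difference in proportions should be reported with it.
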